Our study design incorporates innovative methodological features, including studying if assessing drink size can reduce drinking by itself and if depression modifies e-SBI efficacy. This will provide preliminary information related to how and for whom the e-SBI works. We expect to disseminate our findings via publications in scientific journals and through networks of participating organizations as well as networks of the local county and state perinatal health professionals and substance abuse treatment professionals. Because it begins to build an evidence base for e-SBI efficacy for reducing prenatal alcohol use, our study is of significance for improved maternal and child health. Findings will also impact the larger literature on cost-effective strategies to reduce alcohol-related harm.

Specific aims of the study are to:

- Aim 1. Adapt a computerized SBI (e-SBI) for drinking during pregnancy for use with women of childbearing age.
- Aim 2. Conduct a small randomized trial of the e-SBI with an intervention group (e-SBI, n=100) and a control group (usual care, n=100) at two WIC program sites.
- Aim 3. Use drink size assessment to better measure drinking outcomes, and explore efficacy for the drink size assessment component of the e-SBI.
- Aim 4. Explore if depression modifies alcohol use outcomes for e-SBI. We expect that within the intervention and control group each, women reporting depression will reduce their drinking less than those without depression.

(484 words)

CITATIONS

b) What is the major research question to be addressed in this project?

The study examines efficacy of electronic screening and brief intervention for reducing alcohol consumption among women of childbearing age.

2. Study Procedures: All project types)

a) Describe all study procedures. Please note: The box below is for text only. If you would like to add tables, charts, etc., attach those files in the [Attachment](#) section.

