Development of the computerized study program. Most of the study procedures will be computerized. The computerized study program will include informed consent and all study assessments. It will also deliver the e-SBI to participants who screen eligible and are randomized into the intervention condition, and provide all needed referral information. Thus, the computerized study program will include a) the informed consent b) all study assessments including at baseline, 3 months and 6 months; c) a screening module to identify risky drinkers for study inclusion (those who drink 8 or more drinks in a week or five or more drinks in a day); d) computerized randomization of eligible participants to the two study trial conditions (intervention or the brief alcohol intervention **vs** control or usual care); e) at baseline: a brief alcohol intervention for the intervention group only; f) at the 3-month follow up: a booster (re-administration of) e-SBI for the intervention group; and g) at 3- and 6-month follow up: drink size assessment for both study groups. See study program flowcharts in the attachments for an overview of the modules of the computerized study program.

The Brief Alcohol intervention Like other SBIs, our e-SBI for drinking during pregnancy includes alcohol assessment and feedback, information on alcohol-related harms and benefits of reducing consumption, and a personalized plan for reducing consumption. The plan includes goal setting, an analysis of high risk situations for drinking, and suggested coping strategies. Two components of our e-SBI set it apart from prior interventions: 1) A drink-size assessment that uses *a display of actual drinking vessels (9 glasses) placed above the study computer (see the storyboards for the computerized study program for a picture of the vessels display)*; and photographs or other drink containers (glasses, bottles, cans) to assess beverage-specific drink sizes; 2) Drink size feedback that educates users about standard drink sizes and reviews discrepancies between their drink size and the standard

size for each beverage, highlighting that she may be drinking more than she thinks she does.

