e. Screening Procedures: If subjects will be screened prior to entry into the research, please address the criteria for exclusion and inclusion in the research. Provide reasons for not including women or minorities. Provide justification for including vulnerable populations such as children or prisoners. Please also provide a statement regarding what will happen to the information collected about the individual, should they not enter into the study.

Inclusion Criteria

All consenting non pregnant women who are 18 to 44 years of age and have not been pregnant in the past 6 months will complete a screening using the computerized study program. Given that our study focuses on examining the efficacy of a computerized brief intervention for drinking, women who report at-risk (5 or more drinks in a day) or frequent (8 or more drinks in a week) drinking will be eligible for inclusion in the trial. These criteria are used in prior intervention studies with women of childbearing age due to increased associated risk for birth defects and growth deficiencies. Because, WIC clients are predominantly of minority ethnic status, both women and minorities will be included in the study.

Given recruitment of women of age 18 to 44, the study will include participants ages 18-20. Children below the age of 18 are expected to comprise a small portion (5% or less) of all non-pregnant WIC clinic attendees and will not be included in the study. Women age 18 to 20 are legally considered adults and not minors and can independently consent to medical care and provide informed consent for the study.

While brief interventions are typically not used with drinkers who need more intensive treatment than available in primary care settings, we will not exclude women who report alcohol-related problems. Instead, the computerized study program will provide referral information to participants who report alcohol-related problems as per standard of care at WIC. Usual care at WIC includes providing referral lists with names and phone numbers for diverse health care services, including for alcohol and substance use and depression.

Exclusion Criteria. Pregnant women will not be included in the study as the intervention being studied is for non-pregnant women. Hence if women enrolled in the trial become pregnant after the baseline assessment, we will exclude them from the follow-up assessments.

Screening data and data for participants who do not complete the study.

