The proposed study seeks to reduce excessive alcohol consumption among non-pregnant women of child bearing age as a primary prevention approach to reduce prenatal alcohol use. It is expected to provide important information relevant to public health efforts to reduce Fetal Alcohol Spectrum Disorders and to improve the health of mothers and their infants. The study includes a specific focus on cost-effective methods for screening and brief intervention (e-SBI) and on factors that affect the efficacy of e-SBI. Thus, the proposed study will impact not only public health efforts to reduce drinking in women of childbearing age women, but the larger body of science on the prevention of alcohol-related harm.

Because procedures to adapt e-SBI for use with non-pregnant women involves the input of WIC staff and local experts in maternal and child health, the proposed study will increase networking and collective action among professionals invested in improving women's health. We have already connected with the bay area perinatal advocates and integrated their input into our study implementation and planned dissemination of findings.

Explain why study risks are reasonable in relation to the potential benefits to subjects and to society.

Importance of the knowledge to be gained

There is an urgent need for cost-effective tools for delivering SBI to meet challenges to increase health care access for the implementation of the Affordable Care Act (ACA) in a weak economy with dwindling health care resources. The proposed study will addresses barriers to recommended screening and brief intervention and to the prevention of drinking during pregnancy with a novel electronic SBI to reduce drinking in women before they become pregnant. It will also test if drink size assessment alone can reduce drinking, providing data on possible cost effective interventions. Thus, the proposed study is of significance for the prevention of Fetal Alcohol Spectrum Disorders and for improved maternal and child health. Scientific knowledge on what may reduce or enhance e-SBI efficacy will also impact public health prevention efforts beyond that for childbearing age women and help further refine cost-effective strategies to reduce alcohol-related harm.

8. Administrative Safeguards: (All project types)

a. Are administrative safeguards for data security being met or is there justification for not meeting specific safeguards or providing an alternative safeguard? Yes No

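### The protocol promises to test drink size assessment alone, but no randomised contrast in its two-arm schedule isolates that component

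*Protocol*

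**What the plan says.** **The claim.** In section 7 (Importance of the knowledge to be gained) the protocol writes: "It will also test if drink size assessment alone can reduce drinking, providing data on possible cost effective interventions". The section 1a summary lists "studying if assessing drink size can reduce drinking by itself" among its innovative design features. Aim 3 is milder. Its first half uses drink size assessment to measure drinking outcomes better, and its second half is to "explore efficacy for the drink size assessment component of the e-SBI".

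**The design.** Aim 2 randomises to two groups of 100, the e-SBI and "a control group (usual care, n=100". Section 2a (Development of the computerized study program) sets the schedule:

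- Item e: "at baseline: a brief alcohol intervention for the intervention group only".
- Item f: "at the 3-month follow up: a booster (re-administration of) e-SBI for the intervention group".
- Item g: "at 3- and 6-month follow up: drink size assessment for both study groups".

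The next paragraph of section 2a lists the contents of the e-SBI: alcohol assessment and feedback, information on harms and benefits, a personal plan, drink size assessment and drink size feedback.

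**The control arm.** Section 5e says: "Usual care at WIC includes providing referral lists with names and phone numbers for diverse health care services". Section 6d says that controls receive alcohol assessment only and not the intervention. It adds that assessment by itself has lowered drinking in the control groups of many earlier studies. Section 5e also removes women who become pregnant from the follow-up assessments.

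**The concern.** A test of whether one component works alone needs a group that receives it and a concurrent comparable group that does not, with the two alike in everything else. The schedule contains no such pair. A statistical analysis plan cannot supply one later, because the gap lies in what was randomised.

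Two things are at stake. First, section 7 offers the claim when justifying the risks against the benefits, and links it to possible low-cost interventions. A fall in control-group drinking could then be reported as evidence that the assessment works alone. Second, the control group has had the component by month 6, and the short descriptions in Aim 2 and section 6d do not mention it. A reader of those lines could misjudge what the month-6 comparison compares.

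**Working it through.** The protocol gives no figure for this question, so there is none to reproduce. The check is of what the schedule can identify.

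**Step 1. Exposure before each outcome (section 2a).**

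| Outcome | e-SBI arm has had | Control arm has had |
|---|---|---|
| Month 3 | full e-SBI at baseline | alcohol assessment |
| Month 6 | full e-SBI at baseline and as month-3 booster | alcohol assessment; drink size assessment at month 3 |

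At month 3 the arms differ on five elements at once: alcohol feedback, harm and benefit information, plan, drink size assessment and drink size feedback. At month 6 they still differ on these, with drink size assessment at two earlier visits against one. Randomised contrasts: 2. Contrasts that isolate the component: 0.

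**Step 2. Cell means.** Assume equal baselines by randomisation, no drink size assessment in controls at baseline, and month-3 drinking reported before that visit's drink size module. Let C and I be the control and e-SBI means, D the component's effect in controls at month 6, t3 and t6 all other change in controls, and B3 and B6 the e-SBI effects.

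- C0 = I0 = mu
- C3 = mu + t3
- I3 = mu + t3 + B3
- C6 = mu + t6 + D
- I6 = mu + t6 + B6

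There are five distinct means and six parameters, and the rank is 5. Adding any constant k to t6 and subtracting k from D and B6 leaves every mean unchanged. Estimable: t3, B3, t6 + D, and B6 − D. Not estimable: t6, D, B6. A version in which each assessment visit adds D, with the rest of the bundle left free, also has rank 5 for six parameters, and D is again not estimable.

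**Step 3. What an added assumption buys.**

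- Plateau after month 3 (t6 = t3): D = C6 − C3.
- Linear trend (t6 = 2·t3): D = C6 − 2·C3 + C0.
- Difference: (C6 − C3) − (C6 − 2·C3 + C0) = C3 − C0 = t3.

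If controls fall by x up to month 3 and by x again up to month 6, the plateau credits the component with a reduction of x and the linear trend credits it with nothing. The data cannot choose between them. A third route, B6 = B3, gives D = (I3 − C3) − (I6 − C6). It assumes that the booster and three more months leave the e-SBI effect unchanged.

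**Step 4. Illustration with assumed inputs.** Suppose D = 0 and someone tests the control change from month 3 to month 6 at a two-sided 5% level. In SD units SE = √(2(1 − r)/n), and the rejection rate is Φ(d/SE − 1.96) + Φ(−d/SE − 1.96). With n = 100 and r = 0.5, SE = 0.1. Background drift d of 0.1, 0.2 or 0.3 SD then gives rejection in 17%, 52% or 85% of trials. Over n = 70 to 100 and r = 0.5 to 0.7 the ranges are 13–25%, 39–73% and 71–97%. The documents give no drift, correlation or number analysed, so the verdict does not rest on these figures.

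**Step 5. The month-6 comparison.** It estimates B6 − D. If the component lowers drinking in controls, the contrast shrinks by that amount, which is unknown and may be zero.

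**The case against.** The best defence is that the operative text is already cautious. Aim 3 says explore, section 1a promises preliminary information, and Aim 2 calls the trial small. That stands, and it confines the clear overclaim to section 7 and the closing words of the phrase in the section 1a summary.

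A second defence is that the control arm is not without information. Alcohol assessment precedes both control intervals. The check-in described in section 2a also falls in both, 6 weeks after baseline and 6 weeks after the month-3 interview. The change from baseline to month 3 is therefore an internal reference, and a trend assumption does identify the effect. A reader might infer that no analysis could estimate it unless nothing else changed in controls after month 3, or that the check-in affects only the later interval. The documents support neither reading. The reference is still imperfect: women are selected for risky drinking, so regression to the mean may make the first interval steeper than the second. Reactivity to repeated assessment and loss to follow-up, including exclusion for pregnancy, may also differ between intervals.

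Third, a reader might infer that the control descriptions are false or that the exposure is hidden. Item g states it openly. Drink size assessment can be read as a form of alcohol assessment, and drink size feedback is a separate component that controls are not scheduled to get. Under Aim 3 the assessment also serves outcome measurement in both arms. This defence largely succeeds: the descriptions are incomplete at month 6, not wrong.

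**Conclusion.** The concern holds. The protocol claims to test drink size assessment alone, and neither of its two randomised contrasts does so. The only evidence is the control arm's trajectory, which identifies the effect only under a trend assumption that this schedule cannot check. Two simple choices of trend differ by the controls' entire change from baseline to month 3.

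The absence of an isolating contrast follows from the protocol's text. The finer account of exposure rests on the Step 2 assumptions. That controls have no drink size assessment at baseline is inferred from items e and g; the flowcharts are not shown.

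The control description is a secondary, minor matter. A reader might infer that the month-6 e-SBI result is invalid or known to be diluted. The documents do not show that: the comparison remains randomised, and the size of any shrinkage cannot be derived from them.

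**What to change.** Keep item g, the visits, the sample, the randomisation and the data collected. Change the wording.

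1. **Section 7.** Replace the sentence with: *It will also explore, in a non-randomised analysis of the control group, change in drinking after drink size assessment.*
2. **Section 1a summary.** Replace "studying if assessing drink size can reduce drinking by itself" with *exploring, in a non-randomised analysis of the control group, change in drinking after drink size assessment*, and repeat *studying* before the depression clause.
3. **Aim 3, second half.** For example: *explore, in a non-randomised analysis that cannot establish its efficacy alone, the drink size assessment component.*
4. **Section 6d.** Cross-refer the statement on what controls receive to item g of section 2a.
5. **Month-6 comparison.** Describe it the same way throughout: e-SBI plus booster versus usual care plus alcohol assessment and, from month 3, drink size assessment. Note that any component effect in controls would shrink this contrast by an unknown amount, possibly zero.

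The summary stays within its limit of fewer than 500 words. Change 2 takes 10 words to 16 and adds 1 (+7), and change 3 takes 11 to 16 (+5), so 484 + 12 = 496.

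The cost is a weaker stated claim for the component and ethics-board review of the wording, since section 6f sends changes back for review. The section 15b statement that the aims match the grant should be checked against the reworded Aim 3.
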